8.5 Safety oversight

Safety oversight will be under the direction of a medical monitor, working with the Alliance Pharmaceuticals Ltd. Safety team. The medical monitor is an expert that advises the study investigators and monitors participant safety. The role of the medical monitor is to:

- Review all adverse events on a regular basis throughout the trial
- Be available to advise the investigators on trial-related medical questions or problems
- Evaluate cumulative participant safety data and make recommendations regarding the safe continuation of the study

9 Clinical Monitoring

Conducting Interim Monitoring Visits (IMV) and or Virtual Interim Monitoring Visits; helps verify that the rights, safety and well-being of Study participants are being protected, the Study data is accurate, complete, and verifiable from Source Documents and the Study is being conducted in compliance with the currently approved Protocol/ amendment(s), Good Clinical Practice (GCP), Alliance Pharmaceuticals Ltd. SOPs and site SOPs and other Regulatory requirement(s).

Clinical site monitoring is conducted to ensure that the rights and well-being of human subjects are protected, that the reported trial data are accurate, complete, and verifiable, and that the conduct of the trial is in compliance with the currently approved protocol/amendment(s), with GCP, and with applicable regulatory requirement(s).

A separate Clinical Monitoring Plan (CMP) will be used in this study. The CMP will outline in detail the parameters for clinical site monitoring, including who will conduct the monitoring, the frequency of monitoring, at what level of detail monitoring will be performed, and the distribution of reports.

10 Statistical considerations

The sections below summarize the intended statistical methods and analyses of data for the study.

Descriptive statistical methods will be used to summarize the data from this study, with confidence intervals calculated for the primary and secondary efficacy endpoints. Unless stated otherwise, the term "descriptive statistics" refers to number of subjects (n), mean, median, standard deviation (SD), minimum, and maximum for continuous data and frequencies and proportions for categorical data. All data collected during the study will be included in data listings. Unless otherwise noted, the data will be sorted first by treatment, subject number, and then by date within each subject number.

10.1 Statistical analysis plans

Treatment and control groups will be compared at the primary and secondary endpoints using the proportion of subjects in each group who are lice-free (i.e., no adults or nymphs) as the dependent outcome measure. The proportions for the two groups will be compared using the Z test for independent proportions. In either analysis if the numbers of subjects in the no lice category of either group is less than 10, an alternative estimate of the standard error will be used (e.g., Fisher's Exact or bootstrapping).

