4.1 Description of the Study Design

This is a Study to Evaluate the Safety and Efficacy of Alliance Pharmaceutical Product in Subjects Infested with Pediculosis Capitis. The subject population includes healthy male and female subjects aged 2 years and up who are infested with *Pediculus humanus capitinis*. Household members infestation with an active head lice, defined as at least 1 live louse (adult and/or nymph) present on the scalp and/or hair as determined by a trained evaluator, will receive treatment with study product at baseline.

The planned overall sample size for this clinical trial is approximately n=58 subjects, equally divided between treatment and control groups. Potential subjects will be screened for eligibility and if eligible to participate, their infestation level will be rated. Eligible subjects at each infestation level will be assigned alternately to the treatment or control group to ensure that the two groups have approximately equal representations of infestation severity levels. Level of infestation will be rated as heavy, moderate or light described by how quickly lice were found during combing: heavy infestation = >1 louse with one stroke of the comb; moderate infestation = 1 louse with one stroke of the comb; light infestation = first louse found only after several strokes of the comb

After assignment to a study group, each eligible subject will receive the application of either the Alliance Pharmaceutical Product Vamousse Spray 'n' Go drug or the Permethrin-based control drug. Infested household members will be treated with the Vamousse Spray 'n' Go or Permethrin lotion on-site (i.e., the household members should be assigned to the same treatment as the index case). During the baseline visit (Day 0), the Investigator and clinical staff members will record subject's demographics; elicit informed consent; obtain medical history; review concomitant medication to identify any prohibited therapies the subject may be receiving; collect vital signs; conduct visual assessment of head lice, specifically counting live lice and nits with stages noted, using a 15 inch led 5x magnifying procedure lamp and if needed for confirmation, laboratory microscopes; perform physical examination; assess local skin/ scalp irritation; assess ocular irritation; perform urine pregnancy test on females; and conduct an adverse event assessment.

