7.3 Study schedule

7.3.1 Screening/randomization

Screening Visit Day 0 (Visit 1)

- Obtain informed consent of potential participant verified by signature on written informed consent.
- Record demographic information, obtain medical history, and history of head lice.
- Review medications history and concomitant/prohibited medications to determine eligibility
- Verify inclusion/exclusion criteria.
- Collect urine sample for pregnancy testing for all subjects of childbearing potential.
- Perform assessment for living head lice on subjects and household members for a minimum of 15 minutes. Each subject must have at least 1 live louse. Rate severity of infestation. After each subject has been identified, additional infested household members will also be assessed for infestation.
- Level of infestation will be rated as heavy, moderate or light described by how quickly lice were found during combing: heavy infestation = >1 louse with one stroke of the comb; moderate infestation = 1 louse with one stroke of the comb; light infestation = first louse found only after several strokes of the comb
- Household members must have an active head lice infestation defined as: At least 1 live lice (adult and/or nymph) present on the scalp and/or hair, as determined by a trained evaluator. Household members will be assigned to the same study group as index case.
- Schedule study visits for participants who are eligible and available for the duration of the study.
- Randomly assign subjects to treatment or control group based on infestation severity alternation system (i.e., randomly assign pairs of equal severity levels to treatment and control groups, a form of stratified random sampling) to achieve balanced representation of severity in the two groups.
- Investigational Product Dispensation/ Application for subject.
- Provide each subject with homecare instructions including combing after first wash out.
- Inform subject when to come back for each follow-up visit.
- Provide Standard of Care treatment on-site to unqualified infested household members.

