10.5 Sample Size

Sample size is 52. The requisite sample size for the *t*-test of the means of independent samples, assuming a Cohen's *d* of .40, alpha .05 two-tailed, and a power of .80, was smaller at 44. Thus, the larger requisite sample size for the *z*-test will also suffice for the *t*-test and will provide a cushion for the application of the Holm correction for Type I error. The sample size of 52 should be increased to account for a 10% expected dropout rate, resulting in a total sample size, rounded to an even number, of 58 (26 per group).

Expected difference:

40% difference between treatment groups, based on results of LiceFreee Spray (1% Sodium Chloride) compared to Permethrin; the results showed significantly higher pediculicidal activity for Sodium Chloride spray (85%) as compared to Permethrin (45%) at Day 15 ($p < 0.05$)¹.

A pilot study using Vamousse Spray 'n' Go as a once only treatment, showed high early lice kill (88% lice free at day 0 after treatment) but low efficacy at day 14 (12% lice free). It is anticipated that repeat dosing after 7 days, if live lice are present, will boost day 14 efficacy to levels similar to those at day 0.

Assumptions:

80% power, 0.05 alpha
Allocation ratio 1:1

Methods:

Calculations performed in Stata/IC 16.1
Binary data (lice free – Y/N) – proportions
Independent samples
Chi Squared, two-sided test

Sample:

Estimated sample sizes for a two-sample proportions test
Pearson's chi-squared test
 $H_0: p_2 = p_1$ versus $H_a: p_2 \neq p_1$
Study parameters:

```
alpha = 0.0500
power = 0.8000
delta = 0.4000 (difference)
p1 = 0.4500
p2 = 0.8500
```

Estimated sample sizes:

$N = 52$
 N per group = 26
Allowance for drop out: 10% per group, 3
Total sample: 29 per group (58)

References:

¹ Serrano, L. et al. Evaluation of the Efficacy and Safety of 1% Sodium Chloride (LiceFreee Spray) against 1% Permethrin Crème Rinse on Head Lice Infested Individuals. *Pharmacology & Pharmacy*, 2013, 4, 266-273.

11 Source documents and access to source data/documents

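### Allocation is balanced within infestation severity but the primary Z test ignores it: conservative if severity predicts clearance and subjects are independent, though household clustering could reverse that

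*Combined protocol and SAP*

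**What the plan says.** Section 4.1 rates each subject's infestation as heavy, moderate or light and states: "Eligible subjects at each infestation level will be assigned alternately to the treatment or control group". Section 7.3.1 describes the step differently, as an instruction to "randomly assign pairs of equal severity levels to treatment and control groups, a form of stratified random sampling". Both give balance of severity between the arms as the purpose.

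Section 10.1 sets the primary comparison: "The proportions for the two groups will be compared using the Z test for independent proportions". If either group has fewer than 10 lice-free subjects, it switches to an alternative such as Fisher's exact test or bootstrapping. Section 10.4.2 confirms that only the two group proportions and the two group sizes enter the statistic. The opening of section 10 promises confidence intervals for the primary and secondary efficacy endpoints. Severity appears nowhere in section 10.

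Section 7.3.1 also states: "Household members will be assigned to the same study group as index case". Section 4.1 says the same. Inclusion criterion 6 in the synopsis lets infested household members join the study or receive standard of care. Section 10 does not mention household.

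**The concern.** Balancing on a factor removes that factor's contribution from the true sampling variation of the difference between arms. An analysis that leaves the factor out still counts it in the standard error. If severity predicts clearance, the unstratified Z test then rejects too rarely under the null, and its confidence interval is wider than the design warrants. What is at stake is precision: the allocation scheme buys some, and the planned analysis does not use it.

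Household allocation pulls the other way. Members who take the index case's arm do not enter through their own severity pair. Their outcomes are likely to be correlated. If they are counted as subjects, a test that assumes independence can understate the standard error. The planned test reflects neither feature of the allocation.

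**Working it through.** **1. The plan's own figure.** Section 10.5 gives 45% v 85%, "80% power, 0.05 alpha", "Chi Squared, two-sided test" and "Allocation ratio 1:1". With mean rate 0.65:

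- Uncorrected: n = [1.96·√(2×0.65×0.35) + 0.8416·√(0.45×0.55 + 0.85×0.15)]² / 0.40² = (1.322 + 0.515)² / 0.16 = 21.1, so 22 per group.
- Continuity-corrected: (21.1/4)·[1 + √(1 + 4/(21.1×0.40))]² = 25.9, so 26 per group.

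The stated 26 per group (52) reproduces with a continuity correction that the text does not mention. Dropout: 26/0.90 = 28.9, so 29 per group (58), matching the plan.

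Power of the uncorrected, unstratified test at 26 per group: Φ[(0.40×√26 − 1.322)/0.612] = Φ(1.17) = 87.9%. At 29 per group it is 91.3%.

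**2. Effect of ignoring severity, by hand.** The documents give no lice-free rates by severity and no severity mix. Assume null rates of 90/65/40% in both arms and 9/9/8 pairs.

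- Mean rate = (9×0.90 + 9×0.65 + 8×0.40)/26 = 0.660. The variance used by the Z test is 0.660×0.340 = 0.2245.
- Within-severity variance = (9×0.09 + 9×0.2275 + 8×0.24)/26 = 0.1838.
- True SD of the difference = √(2×0.1838/26) = 0.119. Nominal Z-test SE = √(2×0.2245/26) = 0.131. The ratio is 1.11 before allowing for estimation of the rates.

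Simulation with estimated rates gives an SE about 9% too large. The true size of the Z test is 0.033 to 0.035, against 0.048 to 0.049 for CMH without continuity correction. Strata of 13/8/5 pairs give similar results. The assumed rates imply a light-versus-heavy odds ratio of (0.90/0.10)/(0.40/0.60) = 13.5, a log odds ratio of 2.6.

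**3. Range over the unknown strength of severity.** Simulation with 26 per group, independent subjects, three equal strata and marginal rates held at 45% and 85%. Type I error is at a common 65%.

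| Light v heavy log OR | Z power | CMH power, uncorrected | Z type I error |
|---|---|---|---|
| 0 | 89.3% | 88.6% | 5.6% |
| 1 | 89.7% | 89.6% | 5.1% |
| 2 | 90.5% | 91.6% | 4.0% |
| 3 | 91.7% | 94.3% | 2.8% |
| 4 | 92.5% | 96.5% | 1.7% |

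The gain from stratifying runs from about -1 to +4 points. The continuity correction matters. With 9/9/8 pairs, a corrected CMH has power 81.4% at log OR 0 and 92.4% at log OR 4, against 89.4% and 93.1% for the Z test in the same runs. It was below the Z test in every scenario tried.

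**4. Adding households.** The documents give neither household size nor correlation. Assume a mean of 1.5 or 2 subjects per household, latent ICC 0.23 or 0.50, log OR 1 to 3, and members taking the index case's arm. At 45% v 85% the true SD of the difference was 0.120 to 0.142, against a mean estimated SE of 0.116 to 0.118. Type I error was 4.5% to 10.3% for the Z test and 5.6% to 10.2% for severity-stratified CMH.

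A design-effect check: a mean of 2 per household and ICC 0.3 give 1 + (2 − 1)×0.3 = 1.30, so the true SE is √1.30 = 1.14 times nominal. Naive type I error is 2·[1 − Φ(1.96/1.14)] = 8.6%. A test that allows for the clustering has the power of 26/1.30 = 20 independent subjects per group: Φ[(0.40×√20 − 1.322)/0.612] = 77.7%.

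**The case against.** The best defence is that, with independent subjects, the planned test is valid or nearly so and already exceeds its power target. Nothing in the documents shows that the comb-stroke rating predicts clearance. If it does not, CMH gives up nearly 1 point of power. A CMH test with the continuity correction would be worse than the Z test throughout the range examined. Stratifying also needs rules the plan lacks: what to do with sparse strata, and what replaces the fallback for fewer than 10 lice-free subjects. Dropouts and per-protocol exclusions will also break some pairs.

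Most of this stands, and it limits the point to a modest gain that depends on the CMH variant. It does not justify leaving out the only factor the design balances.

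A reader might go further and infer that the Z test is simply conservative, so that any error is on the safe side. The documents do not support that. Severity-specific rates are absent, and sections 4.1 and 7.3.1 place household members in the index case's arm. With households modelled, the type I error of the Z test was above 5% in most scenarios.

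**Conclusion.** The mismatch between allocation and analysis is plain from the text. Its consequence is conditional. If severity is prognostic and subjects are independent, the Z test is conservative: size about 0.034 and SE about 9% too large under the assumed 90/65/40% rates, and no material overstatement if severity is weakly prognostic. Stratifying changes power by about -1 to +4 points over the range examined.

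A reader might infer that the trial is underpowered because severity is ignored. It is not: under independence the unstratified test has about 88% power at 26 per group against a planned 80%.

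If household members are counted as subjects, the direction can reverse, and adjusting for severity alone does not cure it. How far depends on household size and correlation, neither of which the documents give. The change is worth making to align the analysis with the design, not to rescue power.

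**What to change.** In sections 10.1 and 10.4.2:

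- Make the primary comparison a CMH test without continuity correction, stratified by baseline severity. Report the stratum-weighted risk difference with its 95% CI.
- Prespecify a rule for pooling sparse strata.
- Replace the small-count fallback with an exact stratified test.
- Keep the unstratified Z test as a sensitivity analysis.

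In the same edit, state whether infested household members count toward the 58, and account for household. Either analyse one index subject per household in the primary analysis, or use a household-cluster-robust variance for the stratified risk difference and base the primary test on it. Reconcile section 4.1 (alternation) with section 7.3.1 (random pairs), so that the analysis refers to one defined procedure.

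Cost: the severity part is SAP wording only, because severity is already rated at screening. Its downside is up to about 1 point of power if severity is not prognostic, so it is cheap rather than strictly free. The household part may cost more. If the 58 includes household members at an assumed mean of 2 per household, there are 58/2 = 29 index subjects in all, or about 14 to 15 per group. The one-per-household option would then need more recruitment to reach 26 per group. All of this should be settled before outcome data are seen.

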10.2 Data sets to be evaluated

The subject populations are defined as follows:

Safety Population includes all subjects who were administered treatment. This is the population that will be used for the safety assessments.

Modified Intent-to-Treat (mITT) population includes all subjects who met all inclusion/exclusion criteria, were randomized, administered treatment, and had at least one post-treatment efficacy evaluation. This is the primary population for determination of the effectiveness of the active treatment.

Per-Protocol (PP) population includes all mITT subjects who were administered treatment, had no protocol deviations which could have interfered with the accurate assessment of treatment efficacy, and returned for the Day 14 visit within the allowed window. This is the primary population for the efficacy comparisons between the two active treatment groups.

Subjects whose condition worsens and require alternate or supplemental therapy for the treatment of head lice during the study will be discontinued, included in both the mITT and PP population analyses as treatment failures. Subjects who discontinue early for reasons other than treatment failure will be excluded from the PP population, but included in the mITT population, using Last Observation Carried Forward (LOCF).

Efficacy analyses will be performed on both the per-protocol population and the mITT population. Safety analyses will be performed using the Safety population as defined.

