Statistical Analysis	
ANALYSIS POPULATIONS
 
Safety Population includes all subjects receiving dispensed treatment. This is the population that will be used for the safety assessments.
 
Modified Intent-to-Treat (mITT) population includes all subjects who met all inclusion/exclusion criteria, were randomized, dispensed treatment, and had at least one post-treatment efficacy evaluation. This is the primary population for determination of the kill rate against head lice.
 
Per-Protocol (PP) population includes all subjects who received treatment, had no protocol deviations which could have interfered with the accurate assessment of treatment efficacy, and returned for the Day 14 visit within the allowed window. This population is the secondary analysis.
 
EFFICACY ANALYSIS
 
Primary Efficacy Endpoint The primary efficacy endpoint is the proportion of subjects who are lice free (defined as no live lice, adults or nymphs) 14 days after treatment.
 
Secondary Efficacy Endpoint The secondary efficacy endpoint is the number and percentage of all subjects who are lice-free at Day 2.
 
SAFETY ANALYSIS Descriptive statistics on the severity and duration of adverse events (AEs) from all subjects will be determined for any AE that occurs in at least 5% of the subjects.
 
Analysis of tolerability will be based on scores of Stinging/Burning and Itching sensations collected during Subject Self-Assessment and Source Document at all follow-up visits between the test and reference treatment groups.

PRINCIPAL CONTACTS	South Florida Family Health and Research Centers, LLC. DBA: Lice Cleanique [name], CEO [name] [contact] Mob.: [contact]

	[name], APRN, PI [name] [contact] [contact]
CLINICAL PROTOCOL AND CONDUCT INQUIRIES	Alliance Pharmaceuticals Ltd. [name] R&D Director [contact]
CLINICAL SAFETY INQUIRIES	Alliance Pharmaceuticals Ltd. [name] R&D Director [contact]
PROTOCOL DEVIATIONS	Alliance Pharmaceuticals Ltd. [name] R&D Director [contact]
IRB - Institutional Review Board:	Advarra IRB (Formerly Schulman IRB) [name] [contact] [contact]

2. Study Introduction

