10.3 Statistical hypotheses

Primary Efficacy Endpoint:

Primary Outcome:

The proportion of subjects who are lice free (defined as no live lice, adults or nymphs) at day 14 will be greater in the treatment group than in the control group.

Secondary Outcome:

The mean change between day 14 and baseline in the counts of live lice (i.e., total of live adult lice and nymphs) will be greater in the treatment group than in the control group.

Secondary Efficacy Endpoint:

Primary Outcome:

The proportion of subjects who are lice free (defined as no live lice, adults or nymphs) at day 7 will be greater in the treatment group than in the control group

Secondary Outcome:

The mean change between day 7 and baseline in the counts of live lice (i.e., total of live adult lice and nymphs) will be greater in the treatment group than in the control group.

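### Section 10.2 and the synopsis disagree on whether PP or mITT is primary, so the plan does not settle which set decides the Day 14 superiority test

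*Combined protocol and SAP*

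**What the plan says.** **Section 10.2.** For mITT: "This is the primary population for determination of the effectiveness of the active treatment". For PP: "This is the primary population for the efficacy comparisons between the two active treatment groups". It then adds: "Efficacy analyses will be performed on both the per-protocol population and the mITT population". It does not say which of the two decides.

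**Synopsis, Statistical Analysis.** For mITT: "This is the primary population for determination of the kill rate against head lice". For PP: "This population is the secondary analysis".

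**Hypothesis and test.** Section 10.3 states that the lice-free proportion "at day 14 will be greater in the treatment group than in the control group". Sections 10.1 and 10.4.2 specify a Z test of two independent proportions. Section 10.5 gives the sample size. None of these four sections names an analysis set.

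**How the sets differ.** Under section 10.2, PP excludes subjects with a deviation that could affect the efficacy assessment, subjects who stop early for reasons other than treatment failure, and subjects who do not return for Day 14 inside the window. mITT keeps the non-failure discontinuations by carrying their last observation forward. Subjects discontinued because they need other lice therapy count as failures in both sets.

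**The window.** Section 7.3.4 gives Day 14 as plus or minus 2 days. The synopsis (Study Duration) and section 6.1.7 give plus or minus 3 days for the study as a whole.

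**The concern.** The primary claim is superiority of the spray over permethrin at Day 14. Section 10.2 sends that comparison to PP; the synopsis calls PP secondary. Because the trial is open-label, either set could be presented as the deciding one once outcomes are known, and each choice would have support in the plan.

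The section 10.2 reading has a further weakness. PP membership depends on events after assignment, and some of it is a matter of judgement: section 10.2 does not list the deviations that remove a subject. The arms also differ in what can go wrong. The spray stays in for 8 hours and is washed off and recorded at home, whereas the control is rinsed on site after 10 minutes (sections 4.1 and 6.1.8). PP exclusions could therefore be unequal between arms. That is an inference from the procedures; the documents do not state it.

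**Working it through.** **1. Can the passages be reconciled?** One could read mITT in section 10.2 as the set for a within-arm effectiveness estimate and PP as the set for the comparison. Section 10.2 is then consistent with itself, but the synopsis still calls PP secondary without qualification. The conflict remains.

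**2. Does the sample size settle it?** Inputs from section 10.5: p1 = 0.45, p2 = 0.85, two-sided alpha 0.05, power 0.80, ratio 1:1. The mean rate is 0.65.

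- Uncorrected: n = [1.960·√(2·0.65·0.35) + 0.842·√(0.45·0.55 + 0.85·0.15)]² / 0.40² = 21.1, so 22 per group (44 in total).
- With continuity correction: (21.1/4)·[1 + √(1 + 4/(21.1·0.40))]² = 25.9, so 26 per group (52 in total). This matches the plan's 52.
- Dropout: 26/0.90 = 28.9, so 29 per group (58 in total), in line with "Allowance for drop out: 10% per group, 3".

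The calculation sizes 26 completers per group, which is close to a PP count, but it names no set and so does not resolve the conflict.

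**3. Can the set change the verdict?** A hypothetical example with the pooled two-sided Z test:

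- PP 20/26 v 13/26: difference 0.269, standard error √(0.635·0.365·2/26) = 0.134, z = 2.02, p = 0.044.
- mITT with all six dropouts carried forward as infested, 20/29 v 13/29: difference 0.241, standard error √(0.569·0.431·2/29) = 0.130, z = 1.86, p = 0.063.

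**4. How often?** Exact binomial enumeration. Assumptions: 26 completers and 3 dropouts per arm, dropout unrelated to outcome, dropouts' last readings at the completers' rates, no other PP exclusions, independent subjects, pooled two-sided Z at 0.05. PP uses X ~ Bin(26, p) per arm. mITT with LOCF uses X + Y over 29, with Y ~ Bin(3, p). The 80% and 75% rates are assumptions.

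| Control v test | PP power | mITT-LOCF power | Verdicts differ |
|---|---|---|---|
| 45% v 85% | 89.4% | 91.0% | 4.8% (PP only 1.6%, LOCF only 3.2%) |
| 45% v 80% | 77.5% | 79.6% | 8.0% |
| 45% v 75% | 61.8% | 64.5% | 10.5% |

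Under the null:

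| Common rate | PP alone rejects | Either set rejects |
|---|---|---|
| 45% | 4.8% | 6.3% |
| 65% | 5.5% | 6.7% |
| 85% | 5.6% | 6.9% |

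The excess is about 1 to 2 percentage points. It stays in that range (1.1 to 1.8 points) across common rates from 45% to 85%, with or without the section 10.1 switch to Fisher's exact test when fewer than 10 subjects in a group are lice-free.

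**5. Missing Day 14 counted as not lice-free.** Same model, X/29 per arm, 45% v 85%: power is 82.8% at alpha 0.05. Section 10.5 invokes a Holm correction without stating the number of tests. If there are two (an assumption), the first step is 0.025, and power is 73.9%, against 83.2% for PP and 86.0% for mITT-LOCF.

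**The case against.** The strongest reply is that little turns on this. Section 10.2 requires both analyses, so a discordance could not be hidden. Treatment failures count in both sets, which removes the most damaging kind of PP exclusion. At the planned effect the verdicts differ in fewer than 1 trial in 20, and two-thirds of those cases (3.2 of 4.8 points) are significant only under LOCF, so in this model PP is the harder set to win on. mITT also conditions on treatment and at least one later evaluation. All of this stands and limits the size of the point. None of it says which set decides.

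The figures have limits too. The model contains no deviation or window exclusions. It gives dropouts the completers' Day 14 rates, although the single-treatment pilot in section 10.5 went from 88% lice-free on Day 0 to 12% on Day 14. It also ignores that household members share an assignment (sections 4.1 and 7.3.1).

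Three stronger readings are tempting and not supported:

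- **That PP is shown to favour the spray.** The calculation measures disagreement between overlapping sets, not selection bias, and the documents give no data on PP exclusions.
- **That LOCF is an error, and that counting missing as not lice-free could replace it with power still above 80%.** LOCF is pre-specified, affects only non-failure discontinuations and can bias either way. Replacing it is a separate trade-off, and 73.9% at 0.025 rules out the assurance.
- **That the Day 14 window is stated in three incompatible ways.** Section 7.3.3 shows +2 days, but that is probably a plus-minus sign lost in text extraction: the parallel line in section 7.3.2 has plus-minus, and section 7.3.4 gives plus or minus 2 for the same visit. The 3-day figure is attached to study duration. What remains is at most a 2-day v 3-day clarification.

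**Conclusion.** The point holds. The synopsis and section 10.2 give conflicting rules, and no other section settles which set decides the Day 14 superiority test. Followed literally, section 10.2 rests that test on a set selected after assignment in an open-label trial.

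This should be fixed, but the expected numerical effect is modest: disagreement in about 5% of trials at the planned effect and about 10% at 45% v 75%, with about 1 to 2 points of extra null rejection if either set is accepted. These figures are illustrative and rest on the assumptions in step 4 of the working. More, or unequal, PP exclusions could widen the gap, but the documents do not allow that to be estimated. The finding that the texts conflict needs none of these assumptions.

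**What to change.** - In section 10.2, state that mITT is the single primary population for the Day 14 between-group comparison and that PP is supportive.
- Name that set in section 10.1 or 10.4.2, and bring the synopsis wording into line.
- State one Day 14 visit window for PP membership, reconciling section 7.3.4 with the study-duration figure in the synopsis and section 6.1.7.
- Optionally, add a sensitivity analysis that counts a missing Day 14 assessment as not lice-free. Keep any proposal to replace LOCF as the primary rule separate, and attach no claim that it preserves 80% power.

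The first three changes are wording only. N stays at 52 evaluable and 58 enrolled. The optional analysis uses data already collected. The changes should be made before outcome data are seen.
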